1.3 Sample Size and Power

Planned Sample Size	• Approximately 110 patients will be enrolled in each arm.
Power Statement	• The first dual primary endpoint of this study is the average of 6- and 12- week NT pro-BNP. A generalized linear mixed model with patient as a random effect will be used to estimate the average effect over 6 and 12 weeks controlling for baseline NT pro-BNP and other pre-specified covariates. A gamma distribution with log link will be used to account for the skewed nature of NT pro-BNP. Several sensitivity analyses will be performed, one of which includes site as a random effect to account for clustering of patients within centers. For the first dual primary endpoint a sample size of 110 for each group will achieve 80% power with α =0.05 to detect a difference in NT pro-BNP between the two groups of at least 302 pg/mL from baseline to 12 weeks. The assumptions for this calculation were derived from the BATTLESCARRED trial where the estimated standard deviation for NT pro-BNP was 1250 pg/mL. We expect the standard deviation in the DEFINE-HF Trial to be somewhat lower (961 pg/ml) given lower NT pro-BNP threshold. Of note, 302pg/mL reduction in NT pro-BNP is equivalent to 31.5% of the standard deviation in NT pro-BNP (based on the above assumption). There is an anticipated non-completion rate of approximately 13% so the final sample size per group will be 125.
	 The second dual primary endpoint, the proportion of patients with a ≥ 5-point KCCQ overall summary score increase or a ≥ 20% decrease in NT pro-BNP, averaging over 6 and 12 weeks, will be analyzed using generalized linear mixed models controlling for baseline NT pro-BNP and KCCQ overall summary score as well as several additional covariates as specified below. A binomial distribution with logit link will be used. Several sensitivity analyses will be performed, one of which includes site as a random effect to account for clustering of patients within centers. Power was determined based on comparisons of proportions between two independent groups, where the anticipated control group percent change is 30%. A sample size of 110 for each group will achieve 80% power with α=0.05 to detect an absolute difference in proportions between the two groups of 18% from baseline to 12 weeks for the second dual primary endpoint.

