2.3 Strata, Covariates, and pre-specified subgroup analyses

All efficacy and safety endpoints will be analyzed in the entire cohort, and then within the subgroups of patients with and without diabetes. Analyses for the primary and secondary endpoints will be adjusted for the corresponding baseline measurements as well as history of diabetes (DM), eGFR, and age. A sensitivity analysis will be conducted for each endpoint adjusting for the following additional baseline covariates: AFib type (No AFib, persistent/permanent AFib, paroxysmal AFib) and LVEF (as continuous variable). Restricted cubic splines will be used for continuous variables to accommodate non-linear effects.

Additional sensitivity analysis will repeat the primary analysis but will also include site as a random effect to account for potential clustering by enrolling center. A different sensitivity analysis will use the same model as the primary analysis, but adjust only for the corresponding baseline measurements, without additional covariates.

Additionally, the following pre-specified subgroup analyses will be performed for the primary endpoints (stratified by the baseline variables below):

- Baseline NTproBNP (< median, ≥ median)
- Baseline LVEF (≤30%, > 30%)
- Atrial fibrillation type (No AFib, permanent/persistent AFib, paroxysmal AFib)
- Baseline KCCQ overall summary score (<70, ≥70)
- Baseline eGFR (<60, ≥60 mL/min/1.73 m²)
- Type of cardiomyopathy (ischemic, non-ischemic)
- Age (<65, ≥65)
- Sex (male, female)
- Race (white, black, other)
- Baseline RAASi type (ARNI, ACE/ ARB, neither)
- Loop diuretic dose (Furosemide equivalent mean daily dose: \leq 40 mg, >40 mg)

Subgroup analyses will be carried out by augmenting the primary analysis model with terms for subgroup and a subgroup-by-treatment interaction. Adjusted point estimates and 95% confidence intervals will be calculated for the effect of dapagliflozin compared with placebo within each subgroup. An interaction p-value will be provided.

Due to the large number of study sites and the expected low number of patients per site, site effects will not be explored, although study site will be included as a random effect in efficacy sensitivity analyses to account for within-site correlations, as specified above.

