5.3 Exploratory outcome variables

The following exploratory outcomes will be summarized descriptively for the treatment group and placebo group with outcomes 1-3 on the safety analysis dataset (SAF) and outcomes 4 and 5 on the intention to treat (IIT) dataset. This will be completed first on the entire cohort and then within subgroups of patients with or without diabetes. Continuous measures will be summarized by mean \pm standard deviation and compared using Student's T-tests. Categorical variables will be summarized by frequency and percent and compared using χ^2 or Fisher's exact tests, as appropriate

- 1. Proportion of patients with hospitalizations for heart failure over 12 weeks.
- 2. Proportion of patients with urgent outpatient heart failure visits over 12 weeks.
- 3. Proportion of patients with hospitalizations for heart failure or urgent outpatient heart failure visits over 12 weeks.
- 4. Daily loop diuretic dose (furosemide equivalent).
- 5. Proportion of patients with improved/worsened NYHA Class from baseline at 6- and 12- weeks.

In addition, a Cox proportional hazard model will be used to assess the effect of treatment vs. placebo on the time to the first occurrence for outcomes 1-3, adjusting for history of DM, eGFR, and age. A sensitivity analysis will be conducted additionally adjusting for AFib type (No AFib, persistent/permanent AFib, paroxysmal AFib) and baseline LVEF. A 2nd sensitivity analysis will be performed using stratified Cox proportional model conditional on site to account for clustering. A third sensitivity analysis will be performed using the same approach as the main analysis, but without adjustment for covariates

Daily loop diuretic dose will be analyzed in a manner analogous to that of the first primary endpoint, although appropriate distributions and link functions will be chosen for the given outcomes. Additionally, among patients who were on loop diuretic at randomization, we will also compare the proportion of patients who had loop diuretic dose reduced or discontinued (using the average of 6- and 12-week doses, and also separately at 6 and 12 week timepoints).

Change in NYHA will be analyzed in a manner analogous to that of the first dual primary endpoint, although appropriate distributions and link functions will be chosen for the given outcome.

5.4 Supplemental pre-specified analyses.

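### No Cox model for heart failure events adjusts for baseline NT-proBNP; one pre-specified term would correct chance imbalance in severity and slightly raise power, but would not shrink the standard error

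*SAP*

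**What the plan says.** SAP 5.3 summarizes the heart failure events descriptively and adds a Cox model for each of three outcomes: hospitalization, urgent outpatient visit, and either of the two. The horizon is 12 weeks, as in "Proportion of patients with hospitalizations for heart failure over 12 weeks". The main Cox model estimates the treatment effect "on the time to the first occurrence for outcomes 1-3, adjusting for history of DM, eGFR, and age".

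Three sensitivity models follow:

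- one "additionally adjusting for AFib type (No AFib, persistent/permanent AFib, paroxysmal AFib) and baseline LVEF";
- one stratified by site;
- one "using the same approach as the main analysis, but without adjustment for covariates".

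None includes NT-proBNP.

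The general rule in SAP 2.3 is that primary and secondary endpoints "will be adjusted for the corresponding baseline measurements as well as history of diabetes (DM), eGFR, and age". The same section says of covariate form: "Restricted cubic splines will be used for continuous variables to accommodate non-linear effects".

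On availability, Protocol Table 3 schedules NT-proBNP at both screening and randomization. SAP 2.6 substitutes the screening value in the rare case that the baseline value is missing. SAP 9.2 item 6.2 allows for patients with neither value.

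**The concern.** The common covariate set (diabetes, eGFR, age) is built to sit beside the endpoint's own baseline value. An event endpoint has no such value. The slot is left empty, and the main Cox model carries no measure of heart failure severity.

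The documents treat NT-proBNP as a severity marker elsewhere. It is an entry criterion (Protocol 4.1), a subgroup factor (SAP 2.3), a covariate in both primary models (SAP 5.1.1 and 5.1.2) and part of the laboratory evidence for a heart failure event (Protocol Appendix A).

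If it predicts these events, leaving it out has two effects. The hazard ratio is pulled towards 1, and any chance difference in severity between arms passes into the estimate. Adding the term after unblinding to repair a visible imbalance would look post hoc.

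**Working it through.** **No figure to reproduce.** The documents give no heart failure event rate, hazard ratio or power for these models. The only event expectation is fewer than 10 deaths (SAP 2.6).

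**Inputs from the documents.** 125 per arm ("so the final sample size per group will be 125"), equal allocation, two-sided alpha 0.05, 12 weeks of follow-up.

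**Assumptions.** Placebo 12-week risk 5%, 10% or 15%; treatment HR 0.6 or 1.0; NT-proBNP HR 1.5, 2.0 or 2.5 per SD of the log value.

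**1. What the event count allows.** With d events, SE(log HR) ≈ 2/√d: 0.63 at 10 events, 0.45 at 20 and 0.37 at 30. Power at HR 0.6 is Φ(|ln 0.6|·√d/2 − 1.96). At d = 20 this is Φ(0.511 × 4.472/2 − 1.96) = Φ(−0.82) = 20.7%. At 10 and 30 events it is 12.5% and 28.7%. For 80% power, d = 4(1.96 + 0.842)²/(ln 0.6)² = 31.4/0.261, or 121 events.

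**2. Parameters.** Treatment, diabetes, eGFR and age make 4 if linear; NT-proBNP makes 5. Events per parameter go from 2.5 to 2.0 at 10 events, 5.0 to 4.0 at 20, and 7.5 to 6.0 at 30. If two-parameter splines were used for eGFR, age and NT-proBNP, the total is 8 parameters: 1.2, 2.5 and 3.8 events per parameter.

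**3. Effect of adding the term.** Cox models with treatment, diabetes, eGFR and age, without and then with linear log NT-proBNP, were simulated (250 patients, exponential times, 1,500 trials per setting). Results at HR 0.6 (true log HR −0.511), without → with:

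| Placebo risk | HR per SD | Mean events | Mean log HR | Median SE | Power |
|---|---|---|---|---|---|
| 5% | 1.5 | 10.1 | −0.566 → −0.569 | 0.680 → 0.687 | 6.1% → 6.4% |
| 5% | 2.0 | 10.0 | −0.536 → −0.550 | 0.686 → 0.694 | 7.2% → 7.4% |
| 5% | 2.5 | 10.2 | −0.521 → −0.550 | 0.678 → 0.692 | 5.9% → 7.1% |
| 10% | 1.5 | 19.9 | −0.530 → −0.538 | 0.476 → 0.479 | 18.5% → 19.2% |
| 10% | 2.0 | 20.2 | −0.557 → −0.573 | 0.473 → 0.477 | 19.0% → 20.2% |
| 10% | 2.5 | 20.3 | −0.533 → −0.573 | 0.473 → 0.481 | 17.5% → 18.5% |
| 15% | 1.5 | 30.4 | −0.513 → −0.522 | 0.382 → 0.384 | 24.0% → 26.1% |
| 15% | 2.0 | 30.7 | −0.513 → −0.536 | 0.379 → 0.383 | 24.9% → 25.9% |
| 15% | 2.5 | 31.1 | −0.486 → −0.533 | 0.375 → 0.381 | 22.4% → 26.5% |

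- At 5% risk, 85 to 89 of the 1,500 trials gave no usable fit and are left out.
- Over all 18 settings (HR 0.6 and 1.0) the median SE rose every time, by 0.001 to 0.014.
- At HR 0.6 the estimate moved away from the null by 0.003 to 0.047, and power rose by 0.2 to 4.1 points.
- At HR 1.0 the rejection rate with the term was 3.5% to 5.9%. The Monte Carlo SE at 5% is √(0.05 × 0.95/1,500) = 0.6 points, so there is no sign of inflation.

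A second simulation at HR 0.6, with placebo risks up to 25%, gave gains of about 0 to 1.4 points at 1.5 per SD and 1 to 5 points at 2.2 per SD. Larger gains need stronger assumptions. At HR 0.5, 25% risk (about 49 events) and 2.2 per SD, power went from 56.6% to 64.0%, and the median log HR from −0.63 to −0.69 (true −0.69).

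**4. Chance imbalance.** The arm difference in mean log NT-proBNP has SD √(1/125 + 1/125) = 0.126 SD units. At 2.2 per SD, each SD unit of imbalance moved the log HR by about 0.6 to 0.85 without the term, and by about 0 to 0.2 with it. A typical imbalance therefore shifts the unadjusted log HR by 0.126 × 0.6 to 0.126 × 0.85, or 0.08 to 0.11. In the tenth of trials most imbalanced against dapagliflozin (mean about 0.21), the shift is 0.13 to 0.18. A true HR of 0.60 would then read as about 0.6 × e^0.13 = 0.68 to 0.6 × e^0.18 = 0.72.

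**The case against.** A reader might infer that the omission gives up precision at no saving, on a marker that every patient has. Each part of that fails. The SE rises slightly when the term is added, so the gain comes from the estimate and not from its standard error. Omission saves one parameter, or more under the spline rule. SAP 9.2 item 6.2 foresees patients with no baseline value at all.

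The stronger objections are these:

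- **The shift is not bias in the strict sense.** The hazard ratio is non-collapsible, so the two models target different and equally valid quantities. This stands. With few events, both estimates also drift away from the null, so the adjusted mean is not always nearer the assumed truth.
- **Randomization balances severity on average.** True, but it does not correct the one allocation that occurs. The imbalance argument survives.
- **The gain is negligible with few events.** Largely true: 0.2 to 1.2 points at about 10 events. Patients with a recent heart failure admission or NYHA class IV symptoms are excluded, which makes a high 12-week event rate less likely.
- **The covariate set is coherent.** SAP 2.3 is worded for endpoints that have a baseline value ("Analyses for the primary and secondary endpoints will be adjusted for the corresponding baseline measurements"), and LVEF, itself a heart failure measure, enters one sensitivity model. So the plan does not contradict itself. But that model spends three parameters (two for AFib type, one for LVEF if linear) and still leaves out the trial's own marker.

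**Conclusion.** The point holds as a small improvement to an exploratory analysis. No Cox model for the heart failure events adjusts for baseline NT-proBNP, and the data are nearly complete. Adding it leaves the SE essentially unchanged, reduces attenuation modestly, removes most of the dependence on chance imbalance, and adds about 0 to 5 power points at HR 0.6.

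This rests on assumed placebo risks of 5% to 25% and NT-proBNP hazard ratios of 1.5 to 2.2 per SD. If the marker is weakly prognostic or events number about 10, the power gain is close to zero.

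The covariate choice matters much less than the shortage of events: 121 would be needed for 80% power at HR 0.6, against about 10 to 31 in the tabulated settings. These endpoints have no multiplicity control (SAP 2.5), and no confirmatory conclusion depends on them. The documents do not support calling the planned models invalid.

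**What to change.** In SAP 5.3, before unblinding, add log baseline NT-proBNP to the Cox models for outcomes 1 to 3 as a single linear term, stated as an exception to the spline rule in SAP 2.3. Use the screening value where the randomization value is missing, as SAP 2.6 already does. Keep the unadjusted sensitivity model, which also retains any patient with neither value.

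Do not add a rule that drops eGFR, age or any other covariate if events turn out to be few. Without a fixed threshold it would let the model be chosen after the events are seen.

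The cost is one sentence in the SAP and one more parameter in models likely to have few events. No new data are needed.

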6 SAFETY ANALYSES

Safety analyses will be performed on the safety analysis set (SAF). Total number of adverse events as well as number and proportion of patients developing adverse event(s) will be compared by treatment group. For patient level analyses multiple events will be counted once only per subject in each summary. The following safety variables will be included:

- 1. All cause death
- 2. Cardiovascular death
- 3. Non-fatal myocardial infarction (MI)
- 4. Stroke
- 5. Acute kidney injury (defined as doubling of serum creatinine based on the modified RIFLE criteria)
- 6. Adverse events (AEs).
 - Adverse events of special interest
 - o Diabetic Ketoacidosis
 - Volume Depletion Event (defined as hypotension, syncope, orthostatic hypotension or dehydration)
 - Severe Hypoglycemic Event
 - o Lower Limb Amputations
 - Drug Adverse Event
 - Serious Adverse event
 - $\circ \quad \text{Resulted in death} \quad$
 - In-patient hospitalization or prolonging of existing in-patient hospitalization

- Persistent or significant disability
- Life-threatening
- Congenital anomaly/birth defect
- Important medical event

Safety analyses will be restricted to adverse events that occurred between randomization and 12 weeks. Adverse events occurred between 12 weeks and 13 weeks will be presented separately in a supplemental analysis.

8 SOFTWARE

All analyses will be performed using SAS 9.4 or higher.

9 APPENDICES

9.1 Scoring and Interpreting the KCCQ

There are 10 summary scores within the KCCQ, which are calculated as follows:

A. Physical Limitation

The Physical Limitation score corresponds to questions 1a through 1f. Responses to questions 1a through 1f should be coded numerically as follows:

- 1 = Extremely Limited
- 2 = Quite a bit Limited
- 3 = Moderately Limited
- 4 = Slightly Limited
- 5 = Not at all Limited
- 6 = Limited for other reasons or did not do the activity

If the responses to questions 1a through 1f are not values 1, 2, 3, 4 or 5 then the response is set to missing. Note that a response of 6 (Limited for other reasons or did not do the activity) is treated as a missing value. If at least three responses to questions 1a-1f are not missing, then the physical limitation score is computed by calculating the mean response and standardizing the result as follows:

B. Symptom Stability

The Symptom Stability score corresponds to question 2. Responses to question 2 should be coded numerically as follows:

1 = Much Worse 2 = Slightly Worse 3 = Not Changed 4 = Slightly Better 5 = Much Better 6 = I've had no symptoms over the last 2 weeks

If the response is 6 (no symptoms over last 2 weeks) then set the response to 3 (not changed). If question 2 is not missing then the symptom stability score is computed by standardizing the result as follows:

Symptom Stability = 100*(Response - 1)/4

C. Symptom Frequency

The Symptom Frequency score corresponds to questions 3, 5, 7 and 9. The responses should be coded sequentially (1, 2, 3...) in order of increasing health status as follows:

Question 3

- 1 = Every Morning
- 2 = 3 or more times per week, but not every day
- 3 = 1-2 times a week
- 4 = Less than once a week
- 5 = Never over the past 2 weeks

Questions 5 and 7

- 1 = All of the time
- 2 = Several times per day
- 3 = At least once a day
- 4 = 3 or more times per week, but not every day
- 5 = 1-2 times per week
- 6 = Less than once a week
- 7 = Never over the past 2 weeks

Question 9

1 = Every night

- 2 = 3 or more times a week, but not every day
- 3 = 1-2 times a week
- 4 = Less than once a week
- 5 = Never over the past 2 weeks

If two or more responses are missing then symptom frequency cannot be computed and will be missing. Otherwise, the symptom frequency is computed by calculating the mean of the standardized responses and multiplying by 100 as follows:

Symptom Frequency = 100^{*} Mean((Q3 - 1)/4, (Q5 - 1)/6, (Q7 - 1)/6, (Q9 - 1)/4)

D. Symptom Burden

The Symptom Burden score corresponds to questions 4, 6 and 8. The responses should be coded numerically as follows:

- 1 = Extremely Bothersome
- 2 = Quite a bit Bothersome
- 3 = Moderately Bothersome
- 4 = Slightly Bothersome
- 5 = Not at all Bothersome
- 6 = I've had no swelling (fatigue, shortness of breath)

If a response is 6 (none) then set the response to 5 (not at all). If at least one response is present then symptom burden score is computed by calculating the mean response and standardizing the result as follows:

Symptom Burden = 100^{*} (Mean Response – 1)/4

E. Total Symptom Score

The total symptom score is calculated as the mean of the symptom frequency score and symptom burden score.

F. Self-Efficacy

The Self-Efficacy score corresponds to questions 10 and 11. Responses to questions 10 and 11 should be coded sequentially (1, 2, 3, 4, 5) in order of increasing health status, with 1 denoting the response associated with the lowest health status. If at least one question response is present then the self-efficacy score may be computed by standardizing the mean response as follows:

Self-Efficacy = 100*(Mean Response - 1)/4

G. Quality of Life

The Quality of Life score corresponds to questions 12, 13 and 14. Responses to questions 12, 13 and 14 should be coded sequentially (1, 2, 3, 4, 5) in order of increasing health status, with 1 denoting the response associated with the lowest health status. If at least one question response is present then the quality of life score may be computed by standardizing the mean response as follows:

Quality of Life = 100^{*} (Mean Response - 1)/4

H. Social Limitation

The Social Limitation score corresponds to questions 15a through 15d. These responses should be coded numerically as follows:

1 = Severely Limited
 2 = Limited Quite a bit
 3 = Moderately Limited
 4 = Slightly Limited
 5 = Did Not Limit at All
 6 = Does not apply or did not do for other reasons

If the responses to questions 15a through 15d are not values 1, 2, 3, 4 or 5 then the response is set to missing. Note that a response of 6 is treated as a missing value. If at least two question responses are present then the social limitation score may be computed by standardizing the mean response as follows:

Social Limitation = 100*(Mean Response – 1)/4

I. Clinical Summary Score

The clinical summary score is calculated as the mean of the physical limitation score and total symptom score.

J. Overall Summary Score

The overall summary score is calculated as the mean of the physical limitation score, total symptom score, quality of life score and social limitation score.

9.2 Protocol deviations

Number	Important Protocol Deviations Criteria	Major Impact on Analysis (MIA)/Other	Exclusion level
1. Did not	t fulfil eligibility criteria – inclusion criteria:		
1.1	Ability to provide informed consent prior to initiating screening visit procedures	MIA	Complete exclusion from PPS and MODIFIED ITTS
1.2	Age > 18 and < 120 at the screening visit	Other	No exclusion
1.3	Established diagnosis of heart failure (for at least 16 weeks prior to the screening visit) with reduced systolic function (LVEF≤40% due to either ischemic or non-ischemic etiology) documented by an imaging modality within the past 24 months. Any local measurement of LVEF by any modality within the eligibility range made within the past 24 months is acceptable provided there has been no subsequent LVEF measurement above 40%.	Other	To be decided on a case by case basis
1.4	No change in diuretic management for 1 week prior to screening visit or between the screening and randomization visit	Other	To be decided on a case by case basis
1.5	NYHA class II or III heart failure symptoms at the screening and randomization visit	Other	To be decided on a case by case basis

Number	Important Protocol Deviations Criteria	Major Impact on Analysis (MIA)/Other	Exclusion level
1.6	BNP ≥100 pg/mL and/or NT pro-BNP ≥ 400 pg/mL at the screening visit (For patients with permanent atrial fibrillation inclusion thresholds will be BNP ≥ 125 pg/mL or NTproBNP ≥ 600 pg/mL)	Other	To be decided on a case by case basis
2.0	fulfil eligibility criteria – exclusion criteria: Decompensated heart failure (hospitalization for heart failure within the 30 days prior to screening or NYHA class IV heart failure symptoms at screening)	Other	To be decided on a case by case basis
2.1	History of type 1 diabetes	Other	To be decided on a case by case basis
2.2	Estimated glomerular filtration rate (eGFR) < 30 at the screening visit by modified MDRD equation GFR in mL/min per 1.73 m ² = 175 x SerumCr ⁻ ^{1.154} x age ^{-0.203} x 1.212 (if patient is African American) x 0.742 (if female)	Other	To be decided on a case by case basis
2.3	Admission for an acute coronary syndrome (ST- elevation MI, non-ST-elevation MI, or unstable angina), percutaneous coronary intervention, or cardiac surgery within 30 days prior to the screening visit.	Other	To be decided on a case by case basis

Number	Important Protocol Deviations Criteria	Major Impact on Analysis (MIA)/Other	Exclusion level
2.4	Admission for cardiac resynchronization therapy (CRT) within 90 days prior to the screening visit	Other	To be decided on a case by case basis
2.5	Planned cardiovascular revascularization (percutaneous intervention or surgical) or major cardiac surgery (coronary artery bypass grafting, valve replacement, ventricular assist device, cardiac transplantation, or any other surgery requiring thoracotomy) or CRT within the 90 days after the screening visit.	Other	To be decided on a case by case basis
2.6	Participation in any interventional clinical trial (with an investigational drug or device) that is not an observational registry within the 8 weeks prior to the screening visit.	Other	To be decided on a case by case basis
2.7	History of hypersensitivity to dapagliflozin	Other	To be decided on a case by case basis
2.8	For women of child-bearing potential: Current or planned pregnancy or currently lactating.	Other	To be decided on a case by case basis

Number	Important Protocol Deviations Criteria	Major Impact on Analysis (MIA)/Other	Exclusion level
2.9	Women who are surgically sterile or those who are postmenopausal for at least 1 year are not considered to be of child-bearing potential. Women of child-bearing potential, who are sexually active, must agree to use a medically- accepted method of birth control for the duration of the study. Women of child-bearing potential will have a urine pregnancy test at every clinic visit and it must be negative to continue study participation.	Other	To be decided on a case by case basis
2.10	Life expectancy <1 year at the screening visit	Other	To be decided on a case by case basis
2.11	Patients who are volume depleted based upon physical examination at the time of the screening or randomization visit	Other	To be decided on a case by case basis
2.12	BNP <100 pg/mL and NT pro-BNP<400 pg/mL at the screening visit (For patients with permanent atrial fibrillation exclusion thresholds will be BNP<125 pg/mL and NTproBNP<600 pg/mL)	Other	To be decided on a case by case basis
2.13	Patients currently being treated with any SGLT-2 inhibitor (dapagliflozin, canagliflozin, empagliflozin) or having received treatment with any SGLT-2 inhibitor within the 12 weeks prior to the screening visit.	Other	To be decided on a case by case basis

Number	Important Protocol Deviations Criteria	Major Impact on Analysis (MIA)/Other	Exclusion level
2.14	Average supine systolic BP <90 mmHg at the screening or randomization visit	Other	To be decided on a case by case basis
2.15	Past or current history of bladder cancer	Other	To be decided on a case by case basis
2.16	Active Hematuria	Other	To be decided on a case by case basis
2.17	Donation of blood or bone marrow 12 weeks prior to the screening visit and no planned donations during the study period	Other	To be decided on a case by case basis
2.18	Heart failure due to restrictive cardiomyopathy, active myocarditis, constrictive pericarditis, severe stenotic valve disease, and HOCM (hypertrophic obstructive cardiomyopathy).	Other	To be decided on a case by case basis

3. Patie	ent developed discontinuation of investigational produ	ct criteria bu	t dosing continued
3.0	Subject experienced an Adverse Event which in the opinion of the Investigator and/or AstraZeneca, contraindicated further dosing	Other	To be reviewed on the case by case basis
3.1	Pregnancy confirmed by a positive pregnancy test or other examinations	Other	Complete exclusion from PPS
3.2	Donation of blood or bone marrow during the study period	Other	To be decided on a case by case basis
3.3	Admission for an acute coronary syndrome (ST- elevation MI, non-ST-elevation MI, or unstable angina), percutaneous coronary intervention, or cardiac surgery during the study period.	Other	To be decided on a case by case basis
4. Patie 4.4.1	ent received prohibited concomitant medication but st	1	
4.4.1	SGL12	Other	Only the efficacy endpoints before the start of SGLT2 will be included in modified IITS, OTS, and PPS
5. Patie	ent received incorrect investigational treatment/dose		
5.0	Datient took incorrect treatment or demaged	MIA	
	Patient took incorrect treatment or damaged Investigational Drug Kit		To be decided on a case by case basis
5.1		MIA	

5.4	Overdose	MIA	To be decided on the case by case basis
6. Prote	ocol-required procedure not adhered to:		
6.0	Study data collection has not been stopped when subject decided to withdraw their consent from the study completely	Other	No exclusion from PPS Data collected after consent withdrawal to be excluded from data base
6.1	Patients with absence of NT-proBNP data at randomization visit and having values at Screening visit.	Other	No exclusion from PPS Values from screening visit will be used to impute the values at randomization visit.
6.2	Patients with absence of baseline NT-proBNP data at both screening and randomization visits	Other	Excluded from the NT- proBNP analyses
6.3	Patients with no NT-proBNP values after randomization	Other	Excluded from the NT- proBNP analyses
6.4	Patients with absence of baseline KCCQ summary score at randomization visit	Other	Excluded from the KCCQ analyses
6.5	Patients with no KCCQ overall summary score after randomization	Other	Excluded from KCCQ analyses
6.6	Patients with absence of baseline 6-minute walk assessment at randomization visit	Other	Excluded from the 6- minute walk analyses
6.7	Patients with no 6-minute walk assessment after randomization	Other	Excluded from 6- minute walk analyses
6.8	Patients with missing values in the covariates: age, gender, Hx AFib, AFib type, Hx DM, eGFR at randomization, lvef at randomization	Other	No exclusion from PPS Excluded from the first and second primary analysis
